4.6. Composition of the test product

The test product TripleA consists of an alcohol meter, a mobile phone with an installed app, a micro-USB charger, instructions for use and extra blow nozzles. The blowing nozzle that will be placed in the user's mouth is made of a biocompatible plastic material (Cyclooy HC1204HF-8H5D003).

Ethyl glucuronide (EtG) and ethyl sulfate (EtS) are conjugated ethanol metabolites that are commonly measured in urine samples but can also be measured in blood and hair samples. EtG and EtS in urine are used as markers to detect alcohol consumption or confirm sobriety during the last 24 hours. A minor to moderate alcohol intake can be detected for up to 1 day and intoxication for up to a couple of days afterwards. EtG and EtS are eliminated more slowly than ethanol and therefore they can be used even after the ethanol has disappeared from the body. (Helander 2011).

Phosphatidylethanol (PEth) is a group of membrane lipids formed from phosphatidylcholine in the presence of ethanol and measured in whole blood. PEth is used as a marker to demonstrate regular alcohol consumption and "risk use" or to confirm sobriety in recent weeks (Helander 2011). PEth is specific for alcohol, but does not detect occasional intoxication. The half-life is 4-7 days (Helander 2011, Helander et al 2012). The concentration of PEth-16: 0/18: 1 in the blood reflects the alcohol consumption of recent weeks. PEth-16: 0/18: 1 values lower than 0.05 µmol / L indicate no or low sporadic alcohol consumption. Values between 0.05-0.30 µmol / L speak for regular moderate consumption, but even occasional very large intakes of alcohol can probably give measured values in this range. (Sampling instructions B-Phosphatidylethanol, Karolinska University Laboratory).

Low carbohydrate transferrin (CDT) shows alcohol-induced change in the glycosylation pattern of transferrin, which is measured in serum samples. CDT is used as a marker to demonstrate regular alcohol consumption and «risk use / abuse», where the measured value reflects the intake during the last weeks - the month. Single major alcohol intakes do not affect CDT levels. The specificity is controversial, as an elevated CDT value may have causes other than alcohol.

Within the framework of the current study, PEth and CDT will be analyzed.

4.7. Evaluation of the results of the relevant preclinical tests/assessments performed to justify the use of the test product in human subjects

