If the patient has a valid explanation for the lack of an individual blow, the caregiver can state this in the system, and indicate whether or not there should have been alcohol in the exhaled air at the time in question.

Compliance with the agreed plan for visits to the care provider and / or visits to AA meetings

In cases where the caregiver and patient have agreed that the patient should participate in certain activities, such as e.g. relapse prevention course or MI call, compliance with this plan will be evaluated. The ratio between the number of occasions the patient participated relative to the planned number is calculated and expressed as a percentage. The calculation is made per type of activity, eg:

- The number of treatment meetings that the patient has participated in the last 4 weeks divided by the number of planned treatment meetings for the corresponding period.
- The number of AA meetings visited in the last 4 weeks divided by the agreed number of AA meetings the patient would have attended for the corresponding period.

For the TripleA arm, this information can be retrieved from the TripleA database if that function has been used. However, the comparison between the treatment arms is based on the information noted in the CRF during the visits when the patient is asked about his or her participation. For the TripleA arm, an analysis is then made of how large the correspondence is between the registrations in TripleA and the data in CRF.

Compliance with drug treatment

Adherence to drug treatment will not be evaluated in the context of the study.

Change in the presence of the alcohol metabolites PEth and CDT in the blood at 6 and 12 months, respectively, compared with baseline.

Phosphatidylethanol (PEth) is analyzed at Karolinska Laboratory. The concentration of PEth-16:0/18:1 is given in the unit $\mu\text{mol} / \text{L}$. The PEth level in the blood reflects the alcohol consumption of recent weeks. PEth-16:0/18:1 values lower than $0.05 \mu\text{mol} / \text{L}$ indicate no or low sporadic alcohol consumption. Values between $0.05-0.30 \mu\text{mol} / \text{L}$ speak for regular moderate consumption, but even occasional very large intakes of alcohol can probably give measured values in this range.

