7.3.7. Biological samples (blood and urine)

Samples are ordered via the medical record system, taken and handled according to regular clinical routine. Patients are instructed to leave the samples some week before the visits, so that test results are available for the visit.

For sampling instructions, refer to the latest updated versions on the Academic Laboratory's website.

Urine samples for drug screening usually include amphetamine, benzodiazepines, burprenorphine, cannabis, cocaine, methadone metabolites, opiates. Verification analysis in the event of a positive result on a urine dipstick is performed if clinically relevant

Time: Done at visit 1

Phosphatidylethanol (PEth) is analyzed at Karolinska Laboratory. The concentration of PEth-16:0/18:1 is given in the unit $\mu\text{mol} / \text{L}$. The PEth level in the blood reflects the alcohol consumption of recent weeks. PEth-16:0/18:1 values lower than $0.05 \mu\text{mol} / \text{L}$ indicate no or low sporadic alcohol consumption. Values between $0.05-0.30 \mu\text{mol} / \text{L}$ speak for regular moderate consumption, but even occasional very large intakes of alcohol can probably give measured values in this range.

Time: Made at each visit

Low carbohydrate transferrin (CDT) shows alcohol-induced change in the glycosylation pattern of transferrin, which is measured in serum samples. CDT is used as a marker to demonstrate regular alcohol consumption and «risk use / abuse», where the measured value reflects the intake during the last weeks - the month. Single major alcohol intakes do not affect CDT levels.

Analyzed at the Academic Laboratory and reported in%. Reference interval $<2.0\%$.

Time: Made at each visit

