7.7. Subjects

7.7.1.Inclusion criteria for selection of subjects

- Patients for whom there is a care commitment for the alcohol program at the Addiction and Neuropsychiatry, Akademiska sjukhuset
- 18 years or older
- Meets at least 2 of the criteria for addiction / substance syndrome according to DSM-5
- Ability to understand and communicate in Swedish
- Ability to handle the technical equipment used in the study (breathalyzer + smartphone)
- Has a fixed point (accommodation, night rest place to charge the phone)

7.7.2.Exclusion criteria for selection of subjects

- Schizophrenia
- Substance syndrome related to substances other than alcohol and nicotine
- Impaired lung function (not able to achieve adequate exhalation volume for breathalyzer function)
- The patient is cared for within the framework of LVM
- Unsuitable to participate in the study according to the examiner's assessment
- Has not consumed any alcohol during the 4 weeks that baseline Time Line Follow Back refers to.
- Normalized CDT and PEth values in blood samples taken at visit 1.

7.7.3.Criteria and procedures for removing subjects from the study or suspending their participation

Substance syndrome related to substances other than alcohol and nicotine: Screening with urine sample and DUDIT is done at inclusion. The test result does not have to be available before the subject is included in the study, but should a positive screening test be reported, the subject should be removed from the study. No further samples are taken within the framework of the study.

Should the patient lose or otherwise lose the test product, it can be replaced (a limited number of times) and the patient does not need to be removed from the study if alcohol consumption is reported during the days when the measurements could not be performed and blood tests are performed to determine a new level of PEth / CDT . Phones that have fallen into the wrong hands or are misused in other ways can be deactivated by Kontigo Care. Contact Kontigo Care should this occur.

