7.7.7. Number of subjects to be included in the study

A total of 106 patients are expected to be included in the study, divided 1: 1 between control arm and TripleA arm.

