9.1.2.2. Secondary efficacy endpoints

- i) Change in total amount of alcohol consumed per 4-week period after 6 months from "baseline." An ANOVA model for repeated measurements will be used to compare the groups.
- ii) Change in total amount of alcohol consumed per 4-week period after 12 months from "baseline." An ANOVA model for repeated measurements will be used to compare the groups.
- iii) Proportion of completely sober patients at 12 months A logistic regression model will be used to compare the groups.
- iv) Proportion of completely sober patients at 6 months. A logistic regression model will be used to compare the groups.
- v) Change from baseline in the number of heavy drink days per 4-week period at 6 and 12 months, respectively. An ANOVA model for repeated measurements will be used to compare the groups.
- vi) Change from "baseline" in the number of non-drinking days per 4-week period at 6 and 12 months, respectively. An ANOVA model for repeated measurements will be used to compare the groups. Förändring från "baseline" i antalet standardglas per dryckesdag per 4-veckorsperiod vid 6 och 12 månader, respektive. vii) Time to relapse (ie first alcohol intake). For

patients with the goal of becoming alcohol-free, relapse is defined as the first day after "baseline" where alcohol consumption was found, while relapse for patients with the goal of reducing alcohol consumption is defined as the first day after "baseline" where heavy alcohol consumption is found. Heavy consumption is defined for women as a day with 4 or more glasses, while for men it is defined as a day with 5 or more glasses. The data sources TripleA, TLFB or blood samples are used to detect recurrence. To compare the survival curves, ie. the variable time to recurrence, between the treatment groups a log-rank test will be used.

- vii) CGI improvement. The proportion of respondents at follow-up visits is compared between the groups with a logistic regression model.
- viii) EQ-5D. The groups are compared regarding change from "baseline" with ANOVA model. No significant difference is expected, as quality of life forms are generally not particularly sensitive to change after treatment.
- ix) Participation in treatment. To compare the survival curves, ie. the variable time until the treatment is stopped, between the treatment groups a log-rank test will be used.

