9.2. Sample size, significance level and statistical strength

The primary endpoint is the proportion of patients who do not have heavy drinking days during a 4-week period after 12 months from baseline. Assuming that the proportion is 30% in the control group and you want to be able to detect a difference of 30% between the TripleA and the control group, 42 patients are needed per treatment group to achieve a strength of 80% with a double-sided test of 5% significance level. Assuming that the proportion of patients who do not complete the study is about 20%, a total of 106 patients need to be randomized, ie 53 per group.

Expected loss

The drop-out rate in alcohol studies is usually quite large.

At inclusion, the patient is asked to provide at least one contact person that the study staff can contact if the patient is absent from agreed meetings, interrupts treatment and / or stops blowing. Patients who do not wish to continue their treatment should be informed that they are welcome to continue using TripleA and / or alcohol, or otherwise report their alcohol consumption, as this is valuable information for the study. If the patient wants to stop the study completely, the study staff should at least ask the question "how many standard glasses have you drunk the most in one day since we were last seen?". This gives the opportunity to assess whether there has been a heavy drinking day or not.

A certain loss of patients during the course of the study is expected. Three types of missing data can be identified.

1. Patients who choose to discontinue treatment and study participation.
2. Patients who choose to discontinue treatment but who continue to provide information on alcohol intake (i.e. remain in the study)

Patients who continue treatment but who do not provide complete information on alcohol intake.

4. Patients who miss occasional visits.

All efficacy evaluations will be performed on two analysis populations, a population consisting of all randomized patients contributing efficacy data from at least one baseline visit (ITT) and a population consisting of all patients who completed the study according to the protocol (PP).

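### Time to relapse lists blood samples as an event source, but PEth and CDT can neither date a drinking day nor establish a heavy one, and sections 7.2.2, 9.1.2.2 and 9.1.3 disagree on how the endpoint is derived

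*Combined protocol and SAP*

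**What the plan says.** Section 9.1.2.2 assigns one relapse definition per treatment goal (any alcohol, or a day with at least 4 glasses for women or 5 for men), counts from baseline, and compares the arms with a log-rank test. On sources it says: "The data sources TripleA, TLFB or blood samples are used to detect recurrence". It gives no marker threshold, no rule for change between samples and no rule for turning a blood result into a date.

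Other sections bear on the same endpoint:

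- Section 7.2.2 measures time to relapse by self-report only, and evaluates both definitions rather than one per goal. On PEth of 0.05 to 0.30 µmol/L it says this points to regular moderate drinking, but that "even occasional very large intakes of alcohol can probably give measured values in this range". It adds that one large intake leaves CDT unchanged.
- Section 4.6 says of PEth: "The half-life is 4-7 days". It also says that PEth misses occasional intoxication and that the specificity of CDT is disputed.
- Section 7.3.2 has blood results discussed when the TLFB calendar is completed; the patient's entry is not changed without consent. Only the 4 weeks before each visit are used.
- Section 7.3.7 on timing: "Patients are instructed to leave the samples some week before the visits".
- Section 7.7.2 lists as an exclusion: "Normalized CDT and PEth values in blood samples taken at visit 1".
- Section 9.1.3 plans to compare TLFB-based results with analyses that add blood and TripleA data.

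**The concern.** The endpoint is a number of days to a specific event, and one of the three listed sources does not measure that event. A marker that integrates intake over weeks cannot say on which day a patient first drank, or whether any day reached 4 or 5 glasses. With no rule written down, whoever derives the endpoint must decide, in an open-label trial, whether a raised value is a relapse and which date it gets.

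A further worry is residue. Patients whose markers have normalised are excluded, so those who enter have at least one raised marker at visit 1. Some of the PEth found at month 1 may therefore come from drinking before the study. At stake is the secondary objective in section 6.1.2 of whether relapse can be delayed. The primary endpoint does not use this rule.

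**Working it through.** **The plan's own figure.** No effect size, event count or power is stated for time to relapse. The only sample size is for the primary endpoint (30% against 60%, two-sided 5%, 80% power). With pooled variance:

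n = [1.960 × √(2 × 0.45 × 0.55) + 0.842 × √(0.30 × 0.70 + 0.60 × 0.40)]² / 0.30² = 41.97, so 42 per group.

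42 / 0.80 = 52.5, so 53 per group and 106 in total. This reproduces the plan and is unaffected by the present point.

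**Can blood supply the event?**

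| Needed by 9.1.2.2 | PEth (4.6, 7.2.2) | CDT (4.6, 7.2.2) |
|---|---|---|
| First day with any alcohol | Reflects recent weeks; said to miss occasional intoxication | Reflects weeks to a month; unmoved by one large intake |
| First heavy day | 0.05–0.30 fits both moderate regular and occasional very large intake | As above; may be raised for other reasons |
| A date | None | None |

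Visits at months 0, 1, 2, 3, 6 and 12 are about 30, 30, 30, 91 and 182 days apart. A marker-only event can be placed no more precisely than within such an interval.

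**Residue at month 1.** Inputs: half-life 4 to 7 days (4.6); reference value 0.05 µmol/L (4.6, 7.2.2), which the plan uses for interpretation and not as a relapse criterion; sample about a week before visit 2, so day 30 − 7 = 23, with day 30 as the alternative. For a patient abstinent from visit 1:

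fraction left = 2^(−t / half-life); visit 1 level needed = 0.05 / fraction.

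| Day | Half-life | Fraction left | Visit 1 PEth needed for ≥0.05 |
|---|---|---|---|
| 23 | 4 d | 1.9% | 2.69 |
| 23 | 7 d | 10.3% | 0.49 |
| 30 | 4 d | 0.6% | 9.05 |
| 30 | 7 d | 5.1% | 0.98 |
| 60 | 7 d | 0.26% | 19.02 |

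A start of 0.30 falls to 0.006 (4 d) or 0.031 (7 d) by day 23, below 0.05 either way. By day 60 the level needed exceeds 19, so PEth residue is in practice confined to the month-1 sample. For CDT no half-life is given, so no such figure can be computed.

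The share of abstinent patients affected cannot be fixed, because starting levels are not in the documents. Assuming lognormal starting values (log-SD 0.9, truncated at 0.05), it runs from under 1% (median 0.8, 4 d, day 30) to 89% (median 1.5, 7 d, day 23). That width is the finding; no single value should be quoted.

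**What TLFB covers.** Each visit contributes 28 days. Uncovered time is 91 − 28 = 63 days (9 weeks) between visits 4 and 5, and 182 − 28 = 154 days (22 weeks) between visits 5 and 6. The monthly intervals lose about 30 − 28 = 2 days each.

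**The case against.** A reader might infer that sober patients in both arms will be scored as relapsed at month 1, pulling the two curves together and diluting any difference. The documents do not support that. No section says that PEth of 0.05 or more is an event, or that a sample date is a relapse date. The plan leaves equally open that only a rise counts, or that blood merely prompts the TLFB discussion. Low starting values are plausible: section 7.1.2 notes that some patients have been sober or cut down long before visit 1, and the exclusion as worded may let in a patient with raised CDT and normal PEth. For reduction-goal patients, a residue above 0.05 would not show a heavy day in any case. No hazard ratio or power loss has been computed, and the error runs both ways, since blood also misses isolated relapses.

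It can also be said that the plan nearly has the right structure. Section 7.1.3.2 presents blood sampling as a complement to TLFB, section 7.3.2 feeds results into the interview, and section 9.1.3 sets blood-informed analyses beside the TLFB ones. PEth is described as specific for alcohol, so a clear rise is evidence of some drinking.

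All of this stands and limits the claim. It does not rescue section 9.1.2.2, which puts blood into the event rule of the secondary endpoint itself, contrary to section 7.2.2 and out of line with section 9.1.3.

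**Conclusion.** The point holds as a defect in how the endpoint is derived. Blood samples are a named source for an event that, on the protocol's own description, they can neither date nor, for heavy days, establish, and three sections disagree on the source. This rests on the documents alone.

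Misclassification of abstinent patients at month 1 is possible, not shown. It requires that a raised value counts as an event and that visit 1 PEth was at least 0.49 to 2.69 µmol/L (day 23, half-life 7 to 4 days, first-order decay). The size and direction of any effect on the arm comparison are not established. The change should be made before analysis; it concerns a secondary endpoint and leaves the 106 patients and the primary analysis as they are.

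**What to change.** In section 9.1.2.2:

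1. Remove blood samples as a source of the relapse event or its date in the main log-rank analysis, and date relapse from TLFB drinking days, which exist in both arms.
2. Reconcile sections 7.2.2, 9.1.2.2 and 9.1.3. State whether both relapse definitions or one per treatment goal are analysed, and what day 0 is. Section 7.1.2 lets the baseline period end before visit 1, so counting from baseline does not settle it.
3. Treat a first event that may lie in time not covered by TLFB, chiefly between visits 4 and 5 and between visits 5 and 6, as interval-censored, and name the matching form of the log-rank test.
4. Use PEth only in a pre-specified interval-censored sensitivity analysis, as evidence of any drinking and never of a heavy day. Require a rise over the previous sample by a margin set in advance for assay variation. The visit 1 sample then serves only as a reference value, and a falling residue cannot count.

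The cost is SAP wording, programming for interval censoring and one sensitivity analysis, with no new samples or patients. The downside is that unreported drinking seen only in blood counts only in the sensitivity analysis. A rise rule will also miss steady drinking, or resumed drinking below the earlier level. Blood results still reach the main analysis indirectly, through the TLFB interview.

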3.2. Conventional treatment at the addiction medicine clinic

3.2.1. Relapse prevention

Relapse prevention has its origins in cognitive behavioral therapy (CBT), which is about re-learning and reorientation based on the mapping of dysfunctional thoughts and behaviors.

You can individually or in groups, among other things, handle cravings, say no to alcohol, plan for emergencies and handle incipient relapses. You get to learn about the brain's reward system and problem solving. The concept of post-acute abstinence is highlighted, where the imbalance in the reward system gives different symptoms long after acute symptoms have subsided.

The treatment is usually carried out during eight sessions, each of which takes approximately 45-90 minutes, depending on whether it is individual or in a group. Between the sessions, the participant is given homework that translates theory into practice and provides tools for dealing with everyday life.

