7.3.11. Compliance with treatment and meeting participation

In cases where the caregiver and patient have agreed that the patient should participate in certain activities, such as relapse prevention courses or AA meetings, compliance with this plan will be evaluated. The ratio between the number of occasions the patient participated relative to the planned number is calculated and expressed as a percentage. The calculation is made per type of activity, eg: • The number of treatment meetings that the patient has participated in the last four weeks divided by the number of planned treatment meetings for the corresponding period. • The number of AA meetings visited in the last four weeks divided by the agreed number of AA meetings the patient would have attended for the corresponding period. Time: Done at visits 2, 3, 4, 5 and 6.

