- x) Compliance with TripleA. The proportion of measurements performed by those announced is calculated and reported for the TripleA arm.
- xi) Compliance with the agreed plan for visits to the care provider and / or visits to AA meetings. The treatment groups are compared with respect to the proportion of visits performed based on CRF data with a logistic regression model. For the TripleA arm, the corresponding data collected via TripleA and the correspondence between TripleA and CRF data are also evaluated.
- xii) Alcohol metabolites in the blood. Changes from baseline to 6 and 12 months, respectively, in PEth and CDT levels are calculated and the treatment groups are compared with an ANOVA model for repeated measurements.
- xiii) Evaluation of AUDIT data. The treatment arms will be compared with respect to:
 - xiv) - The proportion of patients who after 12 months have lowered their AUDIT score
 - xv) - The proportion of patients who after 12 months have lowered their AUDIT score to at least one zone
 - xvi) - Proportion of patients who after 12 months have a risk level <II (i.e. less than 6 AUDIT points for women, 8 AUDIT points for men).
- xvii) Evaluation of the number of "reds" and the number of missing blows in TripleA.

TripleA generates new types of high-resolution data that need to be handled in this and future clinical trials. In the simple case, the patient performs all agreed alcohol tests. For these, we can easily calculate the frequency of negative and positive alcohol tests in relation to a limit value for alcohol in the exhaled air. A fully sober patient has then probably performed 90 (3 / day) negative alcohol tests for 30 days in a month and can be considered 100% sober. A positive alcohol test ($> 0.1 \text{ mg / ml} = 0.2 \%$) gives a sobriety that is $1/90 = \sim 99\%$ or if it is calculated per day it will be 96.6% (29/30). What can be more complicated is to correlate this new type of high-resolution data with e.g. the number of days with large consumption from

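### The attendance comparison (Section 9.1.2.2, item xi) names a logistic regression on visits performed and makes no allowance for several visits per patient; if visits are pooled, its standard error is too small

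*Combined protocol and SAP*

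**What the plan says.** Sections 7.2.2 and 7.3.11 define attendance for each patient: "The ratio between the number of occasions the patient participated relative to the planned number is calculated and expressed as a percentage". It is worked out separately for each kind of activity ("The calculation is made per type of activity, eg") over a four-week window, for example "The number of treatment meetings that the patient has participated in the last 4 weeks divided by the number of planned treatment meetings". Section 7.3.11 sets the collection times: "Time: Done at visits 2, 3, 4, 5 and 6". One patient can therefore supply up to five ratios per activity type, each possibly built from several planned occasions.

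The analysis is item xi of Section 9.1.2.2: "The treatment groups are compared with respect to the proportion of visits performed based on CRF data with a logistic regression model". The item does not say whether the unit is the visit or the patient, which of the five windows or which activity type is compared, or how visits of the same patient are handled. No cut-off turns the percentage into a yes/no outcome. No random effect, GEE, robust standard error or overdispersion term appears anywhere in the plan. For PEth and CDT the next item does recognise repeated data ("the treatment groups are compared with an ANOVA model for repeated measurements"), and the drinking changes are treated the same way. Attendance has no counterpart.

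**The concern.** The defined endpoint is a percentage per patient, while an ordinary logistic regression expects independent yes/no outcomes or independent binomial trials. The natural way to apply it to a proportion of visits is to model attended against missed visits. That reading also fits the rest of the section: the primary endpoint and the two sobriety endpoints are proportions of patients, and the CGI endpoint is a proportion of responders, whereas item xi speaks of visits.

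A patient who attends one session is likely to attend the next. If that correlation is positive and ignored, the analysis counts more independent information than 53 patients per arm can supply. Confidence intervals become too narrow and p-values too small. At stake is the credibility of any claimed attendance difference in an open-label trial in which the form of the model could still be chosen after the data are seen.

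**Working it through.** **The plan's own figure.** No sample size or precision is given for attendance. The only figure to reproduce is that of the primary endpoint (Section 9.2): "42 patients are needed per treatment group to achieve a strength of 80% with a double-sided test of 5% significance level". With 30% against 60% and mean 0.45:

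n = [1.96·√(2·0.45·0.55) + 0.8416·√(0.30·0.70 + 0.60·0.40)]² / 0.30² = (1.379 + 0.565)² / 0.09 ≈ 42 per arm.

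Allowing for 20% dropout, 42/0.8 = 52.5, so 53 per arm and 106 in total. The figures reproduce. They supply the number of patients but do not bear on item xi.

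**Inputs for attendance.**
- Patients per arm: 42 evaluable, 53 randomised (Section 9.2).
- m, the planned visits per patient entering the model: not given, so assumed at 1, 2, 4, 5 and 8. Eight is the length of a whole relapse-prevention course (Section 3.2.1), not of a four-week window. Five corresponds to one planned occasion in each of the five windows, pooled.
- ρ, the correlation between visits of one patient: not given, so assumed at 0.1, 0.3 and 0.5.
- Attendance rate, for simulation only: not given, assumed 60% in both arms.

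**Reading 1: attended and missed visits pooled.** The design effect is D = 1 + (m − 1)ρ. The naive standard error is 1/√D of the true one, and a nominal two-sided 5% test has actual type I error 2[1 − Φ(1.96/√D)]. For m = 4 and ρ = 0.3: D = 1.90, standard error ratio 0.73, type I error 15.5%. Each cell gives D, the standard error ratio and the type I error:

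| m | ρ = 0.1 | ρ = 0.3 | ρ = 0.5 |
|---|---|---|---|
| 1 | 1.00; 1.00; 5.0% | 1.00; 1.00; 5.0% | 1.00; 1.00; 5.0% |
| 2 | 1.10; 0.95; 6.2% | 1.30; 0.88; 8.6% | 1.50; 0.82; 11.0% |
| 4 | 1.30; 0.88; 8.6% | 1.90; 0.73; 15.5% | 2.50; 0.63; 21.5% |
| 5 | 1.40; 0.85; 9.8% | 2.20; 0.67; 18.6% | 3.00; 0.58; 25.8% |
| 8 | 1.70; 0.77; 13.3% | 3.10; 0.57; 26.6% | 4.50; 0.47; 35.6% |

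A beta-binomial simulation (4,000 runs per setting, no difference between arms, 53 per arm) gave 8.7%, 16.3% and 22.6% at m = 4, and 12.6%, 26.4% and 35.6% at m = 8. This agrees with the formula.

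**Reading 2: each patient's fraction entered with weight 1.** The model assumes variance p(1 − p), but a fraction based on m visits has variance p(1 − p)·D/m, which is smaller when m > 1 and ρ < 1. The standard error is therefore too large. For m = 4 and ρ = 0.5, D/m = 0.625 and the type I error is 2[1 − Φ(1.96/√0.625)] = 1.3%. Simulation at m = 4 and 8 gave 0.0-1.3%. At m = 2 the same formula gives 0.8% at ρ = 0.1 (D/m = 0.55) and 2.4% at ρ = 0.5 (D/m = 0.75).

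**Patient as the unit.** In the same simulations (42 and 53 per arm), a quasi-binomial model, a robust standard error and a t-test on per-patient percentages all held the type I error at 4.3-5.5%.

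**The case against.** The strongest reply is that item xi is under-specified rather than wrong. It never names the visit as the unit. A GEE or mixed logistic model is still a logistic regression, and so is a model for a yes/no compliance outcome per patient at one visit, which would have no clustering problem. The English text is also visibly a translation, so its wording should not be pressed too hard. This stands in part: a reader might infer that the plan certainly understates the standard error, and the documents do not support that, because the direction depends on the reading. But the plan gives no cut-off that would make the outcome yes/no and no clustering term. An ordinary logistic regression applied to the percentage as defined gives wrong error bars on either remaining reading once a patient has more than one planned visit.

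The size is open to objection too. Within a single four-week window there may be only one or two planned occasions, and then the inflation is nil or modest. The larger figures need several occasions per window or pooling across windows, which the plan neither states nor excludes.

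Two further inferences should be resisted. One is that patients with no planned activity leave an undefined zero-over-zero ratio. Sections 7.2.2 and 7.3.11 already restrict the evaluation to patients with an agreed activity, so at most a patient with an agreed activity but no session in a given window is left open. The other is that the flaw undermines the objective of fewer patients discontinuing treatment. That objective has its own endpoint, time until treatment stops, compared by log-rank test (item ix).

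**Conclusion.** The point holds in conditional form. The model in item xi does not match the endpoint in Sections 7.2.2 and 7.3.11, and nothing in the plan handles several visits per patient. On the natural reading, with visits pooled, a nominal 5% test runs at about 6-11% with 2 visits per patient, 9-22% with 4 and 13-36% with 8, and at 5% with 1. With unweighted per-patient fractions it is too conservative. These ranges rest on assumed visit numbers, assumed correlations of 0.1 to 0.5 and equal numbers of planned visits per patient, so they show what could happen and do not predict this trial. The error bars are wrong as written, but the matter is minor: it concerns one secondary endpoint. The primary analysis uses one binary outcome per patient and is unaffected, as is the retention endpoint.

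**What to change.** Amend item xi to make the patient the unit of analysis, in one of two ways:

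- compare the per-patient attended/planned percentage between arms with a linear model or rank test, one value per patient; or
- keep the logistic model for attended out of planned visits, with GEE or robust standard errors clustered on patient, or a quasi-binomial model with one record per patient.

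In either case, state the activity type and the visit window to be compared, and report per arm how many patients had a planned activity of that type. The cost is a change of wording in the analysis plan. No new data, visits or patients are needed.
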